Table		Page
Table FFAB.4.1.	Objectives and Endpoints	17
Table FFAB.5.2.	Margin of Safety for Intravenous Administration of LY3316531 Based on Administered Dose and Predicted Exposure	21

List of Figures

Figure		Page
Figure FFAB.1.	Protocol I9H-MC-FFAB study design for Cohort 1 and optional Cohort 2.	19
Figure FFAB.2.	Statistical power to detect the primary endpoint of LY3316531 plotted against effect-size for Cohorts 1 and 2.....	43

List of Appendices

Appendix		Page
Appendix 1.	Abbreviations and Definitions	50
Appendix 2.	Clinical Laboratory Tests.....	54
Appendix 3.	Study Governance, Regulatory, and Ethical Considerations	55
Appendix 4.	Hepatic Monitoring Tests for Treatment-Emergent Abnormality	58
Appendix 5.	Blood Sampling Summary	59
Appendix 6.	Protocol Amendment I9H-MC-FFAB(c) Summary A Phase 1 Randomized, Placebo-Controlled Study to Determine the Effect of LY3316531 on Capsaicin-Induced Dermal Blood Flow in Healthy Male Subjects	60

1. Protocol Synopsis

Title of Study:

A Phase 1 Randomized, Placebo-Controlled Study to Determine the Effect of LY3316531 on Capsaicin-Induced Dermal Blood Flow in Healthy Male Subjects

Rationale:

LY3316531 is a humanized bispecific antibody that selectively binds to interleukin-23 (IL-23) and calcitonin gene-related peptide (CGRP). This dual inhibitor is an innovative attempt to target pathways that affect the pathology associated with auto-inflammatory conditions.

This study will assess the activity of LY3316531 on CGRP neutralization via capsaicin-induced dermal blood flow (DBF) as measured using laser Doppler imaging (LDI) in healthy male subjects.

Objective(s)/Endpoints:

Objectives	Endpoints

Primary
 
To assess target neutralization of CGRP following a single IV dose of LY3316531 versus placebo in healthy male subjects via capsaicin-induced DBF as measured using LDI
	
Decrease from baseline within 30 days, relative to placebo, in capsaicin-induced DBF (by blocking CGRP) following at least 1 dose level of a single IV dose of LY3316531

Secondary
 
To assess the safety and tolerability of a single dose of LY3316531 in healthy male subjects
 
To characterize the pharmacokinetics of LY3316531 following IV administration in healthy male subjects
	
Incidence of adverse events, treatment-emergent adverse events, and serious adverse events
 
C_{max} and AUC

Abbreviations: AUC = area under the concentration versus time curve; CGRP = calcitonin gene-related peptide; C_{max} = maximum observed drug concentration; DBF = dermal blood flow; IV = intravenous; LDI = laser Doppler imaging.

Summary of Study Design:

Study I9H-MC-FFAB is a Phase 1 single-site, randomized, subject- and investigator-blind, placebo (Pbo)-controlled, parallel-dose group, single-dose study of LY3316531 (LY) in healthy male subjects. The study will evaluate 1 cohort (Cohort 1) of 16 subjects (12 LY:4 Pbo) with a planned single dose of 300-mg LY3316531 via intravenous (IV) administration. Should an effect not be observed at this starting dose, an optional cohort (Cohort 2) of 12 subjects (9 LY:3 Pbo) may be evaluated with a dose not to exceed 2000-mg IV or the highest tolerable and safe dose evaluated in the single-ascending dose Study I9H-MC-FFAA. All subjects will be invited to attend a follow-up assessment of capsaicin-induced blood flow approximately 160 days post treatment administration.

Treatment Arms and Planned Duration for an Individual Subject:

After a screening period up to 28 days, eligible subjects will be randomized to receive the planned single IV dose of

300-mg LY3316531 or Pbo on the morning of Day 1. Subjects will remain in the CRU for up to 32 hours after study drug administration and attend scheduled visits at the CRU for up to 160 days to assess DBF and measurements for safety, tolerability, and pharmacokinetics (PK). The decision to implement the optional Cohort 2 will be made after reviewing the change in DBF from baseline (relative to placebo) in subjects of Cohort 1 on Day 10 (Figure FFAB.1). The dose to be administered in Cohort 2 will not exceed 2000-mg IV or the highest tolerable dose determined to be safe in Study FFAA.

Number of Subjects:

Cohort 1 is planned to enroll 16 subjects (12 LY:4 Pbo). Optional Cohort 2 is planned to enroll 12 subjects (9 LY:3 Pbo). It is not planned to replace subjects; however, subjects may be replaced if necessary to meet study objectives or at the discretion of the Sponsor.

Statistical Analysis:

Safety: All investigational product (IP) and related protocol procedure adverse events will be listed and, if the frequency of events allows, safety data will be summarized using descriptive methodology. The incidence of treatment-emergent adverse events and serious adverse events will be presented by severity and by association with treatment as perceived by the investigator. Symptoms reported to occur prior to treatment with the study drug will be distinguished from those reported as new or increased in severity during the trial. Safety parameters that will be assessed include laboratory tests, vital signs, electrocardiogram, body weight, immunogenicity, and infusion reactions.

Pharmacokinetics: PK parameter estimates for LY3316531 will be calculated using standard noncompartmental methods of analysis. The primary parameters for analysis will be maximum observed drug concentration (C_{max}) and AUC of LY3316531. Other noncompartmental parameters, such as half-life, apparent clearance, and apparent volume of distribution may be reported. Mean and individual plasma concentration versus time profiles and individual and summary statistics of PK parameter estimates will be generated. Population PK analysis methods may be utilized if necessary.

Pharmacodynamics: Relationships between LY3316531 exposure and capsaicin-induced DBF (absolute and percentage changes), between LY3316531 exposure and total CGRP plasma levels, and between total CGRP plasma levels and capsaicin-induced DBF (absolute and percentage changes) may be explored using graphical- and model-based approaches. Absolute and percentage change in DBF from baseline over all subjects will be summarized by providing the mean, standard deviation, median, minimum, and maximum for plasma drug concentration for each cohort and overall for each sample day and time combination, and maximum over the entire study. Data may be log-transformed prior to summarizing if necessary. The inter-subject and intra-subject variabilities in human pharmacodynamic (PD) responses may also be assessed if appropriate.

Statistical: PK/PD analyses will be conducted on data from all subjects who receive at least 1 dose of LY3316531 and have evaluable PK. If Cohort 2 is conducted, data from like treatment arms across cohorts will be pooled for the purpose of analysis. Pharmacodynamic parameters, and their change from baseline, will be summarized at each applicable visit using descriptive statistics. No statistical inferences will be made and no control for multiplicity is planned. Additional analyses may be performed.

2. Schedule of Activities

Study Schedule Protocol I9H-MC-FFAB

	Screening	Baseline			Postdose								
Visit No.	V1	V2			V3	V4	V5	V6	V7	V8	V9	V10	ED
Study Day	-28 d from Day -2	-1	1	2	10 ± 1 d	24 ± 1 d	38 ± 2 d	52 ± 2 d	66 ± 4 d	80 ± 4 d	120 ± 7 d	160 ± 7 d	
Admission to CRU		X											
Discharge from CRU				X									
Informed consent	X												
Review/confirm I/E criteria	X	X											
Complete medical history	X												
Complete physical examination	X		Predose	X						X			X
Weight	X									X			X
Height	X												
Symptom-directed physical examination			When needed										
Concomitant medications	X		X ^a	X	X	X	X	X	X	X	X		X
Vital signs (pulse rate, blood pressure, and temperature) ^{b,c}	X	X	Predose, EOI, 2 h, 6 h, and 12 h after SOI	24 h after SOI	X	X	X	X	X	X			X
Review preexisting conditions/AEs	X		X ^a	X	X	X	X	X	X	X			X
ECG ^{sc,d}	X		Predose, EOI, and 6 h after SOI	24 h after SOI	X	X		X		X			X
QuantiFERON [®] -TB Gold test or TST	X												

	Screening	Baseline			Postdose								
Visit No.	V1	V2			V3	V4	V5	V6	V7	V8	V9	V10	ED
Study Day	-28 d from Day -2	-1	1	2	10 ± 1 d	24 ± 1 d	38 ± 2 d	52 ± 2 d	66 ± 4 d	80 ± 4 d	120 ± 7 d	160 ± 7 d	
Read TST (if applicable)	X ^e												
Chest X-ray (PA)	X ^f												
HIV/HBV/HCV	X												
Serum chemistry and hematology	X	X		X	X	X	X	X	X	X	X	X	X
Urinalysis	X	X			X	X	X	X	X	X	X	X	X
Ethanol test and urine drug screen	X	X											
Pharmacogenetics (exploratory storage samples for DNA)			Predose										
LY3316531 or placebo administration (IV)			X										
Immunogenicity ^{g,h}			Predose		X	X				X	X	X	X
LY3316531 concentration (PK) ^{g,h}			Predose, EOI, 2 h and 6 h after SOI	24 h after SOI	X	X	X	X	X	X	X	X	X
Target engagement assay (total CGRP)			Predose	24 h after SOI	X	X	X	X	X	X	X	X	X
Capsaicin challenge and LDI ⁱ	X			24-32 h after SOI	X	X	X	X	X	X	X	X	X ^j

Abbreviations: AE = adverse event; CGRP = calcitonin gene-related peptide; CRU = clinical research unit; d = study day; DNA = deoxyribonucleic acid; ECG = electrocardiogram; ED = early discontinuation; EOI = end of infusion; h = hour(s); HBV = hepatitis B virus; HCV = hepatitis C virus; HIV = human immunodeficiency virus; I/E = inclusion/exclusion; IV = intravenous; LDI = laser Doppler imaging; No. = number; PA = posterior to anterior; PK = pharmacokinetics; SOI = start of infusion; TB = tuberculosis; TST = tuberculin skin test; V = visit.

- a At the discretion of the CRU, the baseline measurement for this assessment can be collected at any time after subject admission to the CRU up until just prior to LY3316531 or placebo administration on Day 1.
- b Additional vital sign measurements may be obtained when clinically indicated. Vital signs should be taken following an approximate 5-minute rest in supine position. Temperature measurement is required only at screening and baseline.
- c ECG, vital sign, and PK sampling should occur at approximately the same time. ECG recording and vital sign measurements should occur prior to the blood draw.
- d ECG should be taken following an approximate 5-minute rest in supine position. ECGs are requested to be taken at the specified time; however, aberrations to specified recording times will not be considered protocol deviations as long as the ECGs are taken and the actual recording time is documented. All ECGs will be collected as local safety single ECGs.
- e The follow-up TST reading should occur 2 to 3 days after V1.
- f Not required if chest X-ray was performed within the last 1 year, found to be normal, and report is available. A lateral chest X-ray may be performed if clinically or radiologically indicated.
- g Samples are requested to be taken at the specified time; however, aberrations to specified sampling times will not be considered protocol deviations as long as the samples are taken and the actual sampling time is recorded. It is essential that the actual times of doses and samples are recorded accurately on the appropriate forms.
- h In the event of drug hypersensitivity reactions (immediate or non-immediate), up to 3 additional samples will be collected each for PK and immunogenicity at the following times: 1) as close to the onset of the reaction event as possible, 2) at the resolution of the event, and 3) 30 days following the event.
- i All subjects will have the capsaicin challenge and LDI procedure (pre-challenge and 30 and 40 minutes post-challenge) during a second screening day, V2, and subsequent postdose visits resulting in up to 10 total capsaicin challenges per subject. For each subject, DBF will be measured consistently on the same arm at all study visits.
- j If a subject discontinues from the study early, capsaicin challenge and LDI measurements may be performed at ED if possible, if deemed appropriate by the investigator, and if the most recent capsaicin challenge and LDI measurements for that subject were conducted 7 or more days prior to the ED visit.

3. Introduction

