Because LY3316531 affects the immune system, there is a potential risk it could reactivate an infection such as tuberculosis (TB) or hepatitis B, and could raise the risk that an infection could become more serious than it otherwise would. This risk will be mitigated by screening potential subjects for TB (using QuantiFERON®-TB Gold test and chest X-ray), hepatitis, and human immunodeficiency virus (HIV); and anyone who tests positive in any of these tests will be excluded from the study.

More information about the known and expected benefits, risks, and reasonably anticipated adverse events (AEs) of LY3316531 can be found in the Investigator's Brochure (IB).

There is no anticipated therapeutic benefit for healthy subjects.

4. Objectives and Endpoints

Table FFAB.4.1 shows the objectives and endpoints of the study.

Table FFAB.4.1. Objectives and Endpoints

Objectives	Endpoints

Primary
 
To assess target neutralization of CGRP following a single IV dose of LY3316531 versus placebo in healthy subjects via capsaicin-induced DBF as measured using LDI
	
Decrease from baseline within 30 days, relative to placebo, in capsaicin-induced DBF (by blocking CGRP) following at least 1 dose level of a single IV dose of LY3316531

Secondary
 
To assess the safety and tolerability of a single dose of LY3316531 in healthy subjects
 
To characterize the PK of LY3316531 following a single dose IV administration in healthy subjects
	
Incidence of adverse events, treatment-emergent adverse events, and serious adverse events
 
C_{max} and AUC

Tertiary/Exploratory
 
To evaluate the formation of ADA to LY3316531
 
To evaluate the relationship between LY3316531 exposure and total CGRP plasma levels
 
To evaluate the relationship between LY3316531 exposure and capsaicin-induced DBF
 
To evaluate the relationship between capsaicin-induced DBF and total CGRP plasma levels
	
Presence of ADA against LY3316531
 
E_{max} and EC₅₀ for relationship between LY3316531 exposure and CGRP plasma level
 
E_{max} and EC₅₀ for relationship between LY3316531 exposure and capsaicin-induced DBF
 
Correlation between capsaicin-induced DBF and total CGRP plasma levels

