5.1. Overall Design

[figure not shown]
Study FFAB is a Phase 1 single-site, randomized, subject- and investigator-blind, placebo (Pbo)-controlled, parallel-dose group, single-dose study of LY3316531 in healthy subjects.

After a screening period up to 28 days, subjects will be admitted to the clinical research unit (CRU) on Day -1 and will fast overnight. Subjects will receive a single dose of study drug or Pbo on Day 1 and will undergo the study assessments specified in the Schedule of Activities (Section 2). Subjects may be discharged on Day 2, up to 32 hours after dose administration. In case of safety concerns, subjects will be required to stay in the CRU for a longer period at the discretion of the investigator. Subjects will return to the CRU during the postdose follow-up period (Visits 3 through 10) for a total of 8 follow-up visits through Day 160. For each follow-up visit, subjects will attend the CRU to have the capsaicin challenge and LDI measurement performed along with any other scheduled procedures. These visits are specified in the Schedule of Activities (Section 2) and [Figure FFAB.1](#).

The study will evaluate 1 cohort of 16 subjects (12 LY:4 Pbo) with a planned single dose of 300-mg LY3316531 via IV administration. If no treatment effect on DBF is detected in Cohort 1, an optional Cohort 2 (12 subjects; 9 LY:3 Pbo) may be evaluated with a dose not to exceed 2000-mg IV or the highest tolerable dose determined to be safe in the single-ascending dose (SAD) Study FFAA. The decision to implement the optional Cohort 2 will be made if a sufficiently large decrease from baseline, relative to placebo, in capsaicin-induced DBF is not seen with 300 mg (Cohort 1) within 9 days of the dose (on Day 10). Both cohorts will follow the same admission, treatment, and assessment schedule.

Subjects enrolled will be followed for up to 160 days post treatment administration. It is not planned to replace subjects; however, subjects may be replaced if necessary to meet study objectives or at the discretion of the Sponsor.

Study governance considerations are described in detail in [Appendix 3](#).

Abbreviations: D = day; V = visit.

Figure FFAB.1. Protocol I9H-MC-FFAB study design for Cohort 1 and optional Cohort 2.

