7.7. Concomitant Therapy

In general, concomitant medication should be avoided unless required to treat an AE.

The use of chronic, stable doses of thyroxine is allowed. The use of multivitamins and vitamin C is allowed until 2 days prior to entrance into the CRU. The use of acetaminophen (paracetamol), up to 2 grams per day, is allowed up to 3 days before entrance into the CRU. Thereafter and during the study the investigator may permit a limited amount of acetaminophen for the treatment of headache or any other pain.

Other medication to treat AEs will be prescribed according to the circumstances and guided by the investigator's judgment. If the need for concomitant medication (other than acetaminophen) arises, inclusion or continuation of the subject will be at the discretion of the investigator and Lilly clinical pharmacologist or CRP. In the event medication is used, the name of the drug, the dose and dosage regimen will be recorded in the CRF.

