9.2. Adverse Events

Investigators are responsible for monitoring the safety of subjects who have entered this study and for alerting Lilly or its designee to any event that seems unusual, even if this event may be considered an unanticipated benefit to the subject.

The investigator is responsible for the appropriate medical care of subjects during the study.

Investigators must document their review of each laboratory safety report.

The investigator remains responsible for following, through an appropriate health care option, AEs that are serious or otherwise medically important, considered related to the IP or the study, or that caused the subject to discontinue the IP before completing the study. The subject should be followed until the event resolves, stabilizes with appropriate diagnostic evaluation, or is reasonably explained. The frequency of follow-up evaluations of the AE is left to the discretion of the investigator.

After the informed consent form (ICF) is signed, study site personnel will record, via electronic case report form (eCRF), the occurrence and nature of each subject's preexisting conditions, including clinically significant signs and symptoms of the disease under treatment in the study. Additionally, site personnel will record any change in the condition(s) and the occurrence and nature of any AEs.

The investigator will interpret and document whether or not an AE has a reasonable possibility of being related to study treatment or a study procedure, taking into account the disease, concomitant treatment or pathologies.

A "reasonable possibility" means that there is a potential cause and effect relationship between the IP, study device and/or study procedure and the AE.

Planned surgeries should not be reported as AEs unless the underlying medical condition has worsened during the course of the study.

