9.2.1. Serious Adverse Events

An SAE is any AE from this study that results in one of the following:

- death
- initial or prolonged inpatient hospitalization
- a life-threatening experience (that is, immediate risk of dying)
- persistent or significant disability/incapacity
- congenital anomaly/birth defect
- important medical events that may not be immediately life-threatening or result in death or hospitalization but may jeopardize the patient or may require intervention to prevent one of the other outcomes listed in the definition above.

Study site personnel must alert the Lilly CRP/clinical pharmacologist, or its designee, of any SAE as soon as practically possible.

Additionally, study site personnel must alert Lilly Global Patient Safety, or its designee, of any SAE within 24 hours of investigator awareness of the event via a sponsor-approved method. If alerts are issued via telephone, they are to be immediately followed with official notification on study-specific SAE forms. This 24-hour notification requirement refers to the initial SAE information and all follow-up SAE information.

Investigators are not obligated to follow subjects for AEs or SAEs once they have discontinued from and/or completed the study (the subject summary CRF has been completed). However, if the investigator learns of any SAE, including a death, at any time after a subject has been discharged from the study, and he/she considers the event reasonably possibly related to the study treatment or study participation, the investigator must promptly notify Lilly.

Pregnancy (maternal or paternal exposure to IP) does not meet the definition of an AE. However, to fulfill regulatory requirements any pregnancy should be reported following the SAE process to collect data on the outcome for both mother and fetus.

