10.3.1. Safety Analyses

10.3.1.1. Clinical Evaluation of Safety

All IP and protocol procedure AEs will be listed, and if the frequency of events allows, safety data will be summarized using descriptive methodology.

The incidence of symptoms for each treatment will be presented by severity and by association with IP as perceived by the investigator. Symptoms reported to occur prior to treatment with the study drug will be distinguished from those reported as new or increased in severity during the study. Each symptom will be classified by the most suitable term from the medical regulatory dictionary.

The number of IP-related SAEs will be reported and summarized by preferred term.

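### No adverse-event review is scheduled at Day 120 or Day 160, so AE incidence may be under-ascertained over about the last half of follow-up

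*Protocol*

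**What the plan says.** **Schedule of Activities (Protocol Section 2).** The row "Review preexisting conditions/AEs" is marked at screening, Day 1, Day 2, V3 to V8 and early discontinuation (ED). It is empty at Day -1, V9 and V10. Concomitant medications are marked at V9 but not at V10. Chemistry and hematology, urinalysis, immunogenicity, PK, total CGRP and the capsaicin challenge with laser Doppler imaging are all marked at both V9 and V10.

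**Purpose of the late visits.** The synopsis has subjects attend "scheduled visits at the CRU for up to 160 days to assess DBF and measurements for safety, tolerability, and pharmacokinetics (PK"). Section 5.1 counts V3 to V10 together, "for a total of 8 follow-up visits through Day 160".

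**Endpoint.** Section 4 gives the safety endpoint as "Incidence of adverse events, treatment-emergent adverse events, and serious adverse events", with no end day.

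**Recording duty.** Section 9.2, which applies from consent onwards, says: "Additionally, site personnel will record any change in the condition(s) and the occurrence and nature of any AEs". Section 9.2.1 sets the end point: "Investigators are not obligated to follow subjects for AEs or SAEs once they have discontinued from and/or completed the study".

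**Related text.** Section 7.7 says: "In general, concomitant medication should be avoided unless required to treat an AE". Section 10.3.1.1 says: "All IP and protocol procedure AEs will be listed". Section 10.3.5 allows, but does not require, an assessment of antibodies against safety.

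**SAP.** Section 5.1 still gives follow-up as up to 80 days. Section 6.8.1 plans a table of TEAEs by week and names no last week. The SAP is dated October 2018; protocol amendment (c) was approved in February 2019.

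**The concern.** Section 9 refers to the Schedule for procedures and their timing. A site that follows the Schedule exactly will bring subjects in at Day 120 and Day 160, draw blood and run the capsaicin challenge, yet have no scheduled step at which to ask about AEs. A duty to record what comes to light does not ensure that anyone asks.

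Three things are at stake.

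- AE incidence is a named secondary endpoint. If ascertainment changes at Day 80, incidence over the whole study mixes actively sought events with events that happen to be volunteered or noticed.
- The late period is not pharmacologically quiet. Section 5.4 attributes the Day 160 follow-up to the long duration of the PD effect, and the rationale for amendment (c) in Appendix 6 reports continuing inhibition in many subjects at Day 120.
- Other parts of the plan lean on this information. Procedure-related AEs are to be listed, but the V10 challenge has no scheduled AE review on or after the day, and the V9 challenge has one only if the subject later has an ED visit. If antibodies are related to safety, the V9 and V10 antibody results will have no same-visit AE review beside them.

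A subject who leaves early has a scheduled AE review at ED. A subject who completes has none at the final visit.

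**Working it through.** The plan gives no figure of its own on this point. The check is a reading of the Schedule followed by simple interval arithmetic.

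**1. Are the blanks real?** The Schedule has 13 columns: V1, Day -1, Day 1, Day 2, V3 to V10, ED. The AE-review row has 13 cells, with empty cells at Day -1, V9 and V10. The concomitant-medication row also has 13 cells, empty at Day -1 and V10. The chemistry, immunogenicity, vital-sign and capsaicin rows have 13 cells too. The blanks are therefore not a column shift from text extraction.

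**2. Coverage.** AE review is marked at 6 of the 8 follow-up visits (V3 to V8) and at 0 of the last 2.

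**3. Time after the last scheduled review.** Windows from the Schedule: V8 = Day 80 ± 4 (76 to 84); V9 = Day 120 ± 7 (113 to 127); V10 = Day 160 ± 7 (153 to 167). Dosing is on Day 1, so elapsed time to V10 is its study day minus 1.

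| Case | V8 to V10 (days) | Elapsed to V10 (days) | Share |
|---|---|---|---|
| Nominal | 160 - 80 = 80 | 159 | 50% |
| Shortest | 153 - 84 = 69 | 152 | 45% |
| Longest | 167 - 76 = 91 | 166 | 55% |

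Dividing by study-day number instead gives 69/153 = 45% and 91/167 = 54%; the choice does not matter.

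**4. Comparison with the earlier schedule.** Nominal gaps between post-dose reviews up to V8 are at most 14 days. The longest gaps the windows allow are:

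- Day 2 to V3: 11 - 2 = 9
- V3 to V4: 25 - 9 = 16
- V4 to V5: 40 - 23 = 17
- V5 to V6: 54 - 36 = 18
- V6 to V7: 70 - 50 = 20
- V7 to V8: 84 - 62 = 22

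So even the shortest final gap (69 days) is about three times the longest earlier one (69/22 = 3.1).

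**5. Partial cover from the V9 medication check.** Because Section 7.7 largely restricts medication to treating AEs, asking about medication at V9 can reveal treated AEs. For those, the interval with no scheduled enquiry runs from V9 to V10: nominally 160 - 120 = 40 days, from 153 - 127 = 26 to 167 - 113 = 54. Untreated AEs get no such cover.

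**6. What falls at visits without AE review (not counting ED).** Post-dose capsaicin challenges are on Day 2 and at V3 to V10, 9 in all; 2/9 = 22%. Scheduled post-dose antibody samples are at V3, V4, V8, V9 and V10, 5 in all; 2/5 = 40%.

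**7. Effect of the fix.** With AE review marked at V9 and V10, coverage becomes 8 of 8, and the 80-day nominal gap becomes two of 40 days.

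**The case against.** The strongest opposing reading is that the blanks are a deliberate taper. Vital signs, ECG, weight and complete physical examination also stop at V8 apart from ED, the SAP's vital-sign tables (6.8.3) end at Day 80, and the synopsis describes the Day 160 visit as an invited assessment of blood flow. The synopsis wording on safety does not require every safety measure at every visit, and laboratory tests and immunogenicity, which are safety parameters, continue to V10.

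Other safeguards also exist. Section 9.2 keeps AE recording open without a visit limit and requires documented review of each laboratory report. Section 9.4.4 has the sponsor monitor safety throughout, including infections. Staff are present for the 30- and 40-minute scans and may see acute reactions.

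Finally, the consequence may be modest. Safety analysis is descriptive, the Cohort 2 and Phase 2 decisions use data to Day 10 or Day 24, and half of calendar time is not half of AE risk after a single dose.

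Most of this stands as mitigation. The documents do not say whether the taper was intended or the row was simply not extended when visits were added. But none of these provisions creates an occasion for asking subjects about symptoms between visits. Laboratory review does not reveal untreated symptoms, and sponsor monitoring sees only what the site has recorded. Nor does any text say that active AE enquiry should end at Day 80, while the endpoint carries no such limit.

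**Conclusion.** The concern holds. No AE review is scheduled for the last 80 nominal days (69 to 91 with windows), 45% to 55% of the post-dose period, although subjects attend two visits in that time. AE incidence may therefore be under-ascertained after Day 80.

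The finding has limits. AE recording does not stop at Day 80; what is missing is scheduled enquiry. The number of events missed cannot be estimated from the documents, and the 22% and 40% figures count challenges and samples, not missed events. The schedule is the same in both arms, and subjects and investigators are blind, so no bias between arms is shown. The conclusion assumes that sites follow the Schedule as printed; a site that asks about AEs at every visit as routine would narrow the gap.

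This should be corrected because the endpoint is named, the late period was added on account of a persisting drug effect, and the remedy is cheap.

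**What to change.** - **Schedule of Activities:** mark AE review at V9 and V10, and concomitant medications at V10.
- **Subjects already past V9:** the rationale for amendment (c) shows that some Day 120 visits had taken place. For these subjects, ask at V10 about the whole interval since the last review and record onset dates.
- **SAP 5.1:** change the follow-up from 80 to 160 days. The SAP predates amendment (c), so this is alignment.
- **SAP 6.8.1:** state that TEAE summaries run to Day 160. Its TEAE definition sets no end date, so late events already qualify; the sentence removes doubt.
- **Study report:** if late reviews were not done for some subjects, say that their AE ascertainment after Day 80 was not by scheduled review.

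The cost is one Schedule edit, two short SAP sentences and a few minutes at two visits subjects already attend. AE counts may rise slightly, and subjects first asked at V10 will have to recall up to 91 days.
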